1.3. OBJECTIVES

Primary Objective: To investigate the safety of Silverlon® dressing in patients throughout their prescribed course of radiation therapy and after radiation therapy.

- Hypothesis: We do not expect any adverse effects from extended use of Silverlon® dressing during and after radiation therapy.
- Primary Outcome Measures: Adverse reactions/events documented by the radiation oncologist as "probable" or "definite" related to Silverlon® Dressing (Weekly AE/Chart Review Source Doc).

Secondary Objective: To evaluate the feasibility of managing radiation dermatitis with Silverlon® dressing.

- Hypothesis: We expect that Silverlon® will be a feasible therapeutic modality for managing radiation dermatitis. We expect high compliance rate during RT and slightly lower when skin symptoms are not presented (i.e., before RT and post-RT). We do not expect any withdrawals due to adverse reactions to the dressing.
- Secondary Outcome Measures: Compliance; Withdrawal rate due to dressing.

Exploratory Objective: To monitor the severity of radiation dermatitis and patient quality of life during use of Silverlon® dressing throughout radiation therapy and after radiation therapy.

• Exploratory Outcome Measures: radiation dermatitis severity (RTOG Score & Radiation Induced Skin Reaction Assessment Scale (RISRAS)); DLQI

Page 7 of 41 RSRB STUDY00004587 Version Date: 09/14/2021 NCT04238728

[figure not shown]

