2. STUDY DESIGN

2.1. OVERVIEW

This is a single-site, non-blinded, non-randomized safety study of patients undergoing radiation therapy for breast cancer. This safety study will be conducted by University of Rochester Medical Center in the Departments of Dermatology & Radiation Oncology. Radiation therapy treatment will be delivered at The University of Rochester Medical Center. The study will not address radiation dose, scheduling or application method, which will remain the province of the attending radiation oncologist. The single intervention will be the application of Silverlon® dressing over the radiation site (i.e., whole irradiated breast area) which will start on the first day of radiation therapy and continue for 2 weeks after completion of radiation therapy. The patients will wear the Silverlon® dressing all of the time, except while bathing/showering and during radiation therapy sessions. All study visits and evaluations will take place at times already scheduled for radiation therapy and will not involve additional travel solely for research purposes. Subject participation will start just prior to the start of their prescribed course of radiation therapy and will be completed 2 weeks following completion of radiation therapy. There are no control or placebo groups.

Page 8 of 41 RSRB STUDY00004587 Version Date: 09/14/2021 NCT04238728

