- 90-day Follow-Up: This follow-up by phone call, MyChart message or paper mail will occur 90 days from the start of RT and be scheduled with the subject at their 2-week Post-RT Visit. One or all three methods will be used to contact the subject as needed to complete the follow-up. Message text for copy/paste into MyChart has been included in Appendix A. For completion of the follow-up by paper mail, a pre-addressed and stamped envelope will be provided for the return of the paper response. For safety assessment, FDA recommends following patients up to 90 days. Study personnel will contact the subject to document an adverse reactions or skin reactions in the radiation treatment area to which Silverlon dressing was applied. Study personnel will ask the following questions: 1) Since your 2-Week Post-RT visit, has your skin reaction in the area where the Silverlon® dressing was applied improved, stayed the same, or worsened?; 2) Do you have any skin pain in the area where the Silverlon® dressing was applied? (yes/no); 3) Do you have any itching in the area where the Silverlon® dressing was applied? (yes/no); 4) Do you feel like your skin in the radiation treatment area has fully recovered? (yes/no); and 5) Would you recommend Silverlon® dressing to other patients during radiation therapy? (yes/no). For question 1, if the subject answers "worsened", study personnel will document the description of the skin reaction and notify the treating radiation oncologist to follow-up with the subject.

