- Current hormone treatment (yes/no)
- Current Herceptin treatment (yes/no)
- Body Mass Index (BMI)
- Fitzpatrick Skin Type
- Surgery before RT (yes/no)
- Current Medications

Page 22 of 41 RSRB STUDY00004587 Version Date: 09/14/2021 NCT04238728 Weekly AE/Chart Review Source Doc: This is an electronic REDCap form for collection of any radiation treatment changes, skin changes, or adverse reactions documented by the treating radiation oncologist in the EMR chart note for the patient's weekly clinic visit. Study personnel will review the EMR chart note and report any documented any adverse reactions, skin changes, and/or radiation treatment changes in the form. The following information will be collected on the form:

- Changes in prescribed radiation treatment (yes/no; if "yes", then description of change)
- Documentation of skin changes in radiation treatment area (yes/no)
- Occurrence of adverse event in radiation treatment area to which Silverlon® dressing was applied
- Description of the adverse event
- Date of onset
- Serious (Yes/No)
- Intensity (Mild/Moderate/Severe)
- Relation to Study Drug (Definite/Probable/Possible/Unlikely/Unrelated)
- Action with Study Drug (No Action/Interrupted/Stopped Entirely).

Questions Log: This log will be an electronic REDCap form that collects the answers to the questions asked to the patient by phone, email, or in study visits (as preferred by the subject). Study personnel will ask the subject: 1) Are you wearing Silverlon dressing while you are sleeping? (yes/no); 2) Are you having any discomfort while wearing the Silverlon dressing? (yes/no); and 3) Are you having any adverse reactions to the Silverlon dressing? (yes/no). If the subject answers "yes" to question 3 regarding an adverse reaction to Silverlon, study personnel will document a description of this reaction in the space provided on the form.

RTOG Score: The RTOG toxicity criteria is one of the most commonly used scales for radiation-induced skin reactions (21, 22). The radiation oncologist will rate the skin reaction in the area where Silverlon® dressing was applied in person using the RTOG scale below. The RTOG scores will completed on paper and then entered electronically into REDCap:

RTOG SCALE

0	1	2	3	4	5
No change	Faint erythema,	Tender or bright	Confluent moist	Ulceration,	Death
	dry	erythema,	desquamation in	hemorrhage,	
	desquamation,	moderate	areas other than	necrosis	
	epilation,	edema, patchy	in skin folds,		

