10.2. RECORDING ADVERSE EVENTS

Study personnel will assess adverse events by recording all voluntary complaints of the subject. Any side effects and adverse reactions will be noted on the AE Source Doc. Study personnel will check with the nurse and/or treating radiation oncologist regarding any reported adverse reactions. All adverse events, whether observed by the Investigator, the treating radiation oncologist, or volunteered by the subject, will be documented. Adverse events will be reported per the University of Rochester Research Subjects Review Board (RSRB) reporting requirements. Each adverse event will include a brief description of the experience, the date of onset, the severity of the event, the relationship to investigational intervention, and any action taken with respect to the study and intervention. Adverse event monitoring will occur at the start of informed consent until completion of the study.

The relationship to the study device and the severity of each adverse event (i.e., attribution) as judged by the investigator or radiation oncologist must also be recorded. An adverse event is any untoward medical occurrence in a subject administered study device, and which does not necessarily have a causal relationship with this treatment. The relationship of each adverse event to the study device must be recorded as one of the choices on the scale below:

DEFINITE: Causal relationship is certain (e.g., the temporal relationship between device use and the adverse event onset/course is reasonable; there is a clinically compatible response to dechallenge; other causes have been eliminated; and the event must be definitive pharmacologically or phenomenologically using a satisfactory re-challenge procedure, if necessary).

PROBABLE: High degree of certainty for causal relationship (e.g., the temporal relationship between device use and the adverse event onset/course is reasonable; there is a clinically compatible response to de-challenge [re-challenge is not required]; and other causes have been eliminated or are unlikely).

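### The plan gives no defined route from the 90-day safety contact to the primary outcome, so late dressing-related reactions may be missed or left unattributed

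*Combined protocol and SAP*

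**What the plan says.** Section 1.3 sets the primary objective as safety "throughout their prescribed course of radiation therapy and after radiation therapy", with no end date. The primary outcome is reactions or events that the radiation oncologist documents as probable or definite, "related to Silverlon® Dressing (Weekly AE/Chart Review Source Doc". Section 5.3 shows that this form records onset date, seriousness, intensity and a five-level attribution: "Relation to Study Drug (Definite/Probable/Possible/Unlikely/Unrelated".

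Section 5.1 describes the 90-day follow-up by phone, MyChart or mail and gives its reason: "For safety assessment, FDA recommends following patients up to 90 days". Its stated task is to document adverse or skin reactions in the treated area. The subject answers five questions: change in the skin reaction since the 2-week visit, pain, itch, full recovery, and whether she would recommend the dressing. Only if the first answer is *worsened* does anything follow: "study personnel will document the description of the skin reaction and notify the treating radiation oncologist to follow-up with the subject".

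The schedule in section 15 marks the Weekly AE/Chart Review Source Doc weekly during RT and at the Mid-Study, EndRT and 2-Week Post-RT visits. At day 90 it marks only the 90-Day Phone Call Form.

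On timing, section 2.1 says that participation "will be completed 2 weeks following completion of radiation therapy", and section 10.2 says "Adverse event monitoring will occur at the start of informed consent until completion of the study".

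**The concern.** A contact made for safety assessment should be able to feed the safety outcome. Here the two are not joined. A subject who reports itch at day 90 under the dressing area gives an answer that no one is told to assess, on a form with no place for attribution, at a time when event monitoring may already have ended. Section 13 names no analysis of the 90-day answers.

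The plan expects zero events, and its data are meant to support a 510(k) application for the radiation dermatitis indication. With an expected count of zero, one attributed event changes the result, so whether late reactions are captured matters more than it would in a study expecting many events.

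**Working it through.** **1. What a primary event needs, and what day 90 supplies** (sections 1.3, 5.1, 5.3, 15 and Appendix A)

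| Element | Visits up to 2 weeks post-RT | 90-day contact |
|---|---|---|
| Subject asked about adverse reactions to the dressing | Yes (Questions Log) | Not among the five questions |
| Radiation oncologist assesses | Yes | Only after *worsened* |
| Form with attribution, seriousness, intensity | Scheduled | Not scheduled; 90-day form has no such fields |
| Within the adverse event window | Yes | Depends on the reading (step 2) |

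Pain and itch are asked in the present tense. A reaction that began after the 2-week visit and had resolved by day 90 need not surface.

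**2. When the window closes**

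- Reading A, two weeks post-RT: section 2.1 ends participation there. Section 5.2, on dispensing dressings, glosses study completion the same way. Section 10.2 ties event monitoring, and section 10.3 ties serious event reporting, to completion.
- Reading B, day 90: section 5.1 places a safety contact there, and note 6 to the schedule says FDA requested it so that subjects are monitored up to 90 days. In section 5.3 the Comprehensive Study Log lists the 2-week visit and study completion as separate items.

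The documents do not choose between the two.

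**3. The plan's own precision figures** (section 13.1, exact Clopper-Pearson, two-sided 95%)

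For 0 events the upper limit is 1 − 0.025^(1/n).

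- n = 30: 0.1157, printed as 0.116.
- n = 36: 0.0974, printed as 0.097.

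Both reproduce, so there is no arithmetic error on this point.

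**4. Effect of a late event, as illustration only**

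For x events the limits are the 0.025 quantile of Beta(x, n − x + 1) and the 0.975 quantile of Beta(x + 1, n − x).

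| Late events | n = 36 | n = 30 |
|---|---|---|
| 0 | 0 to 0.097 | 0 to 0.116 |
| 1 | 0.001 to 0.145 | 0.001 to 0.172 |
| 2 | 0.007 to 0.187 | 0.008 to 0.221 |

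**5. Calendar time after the last scheduled attribution form**

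Section 3.5 allows 15 to 40 fractions. Assumption, not in the documents: five fractions a week from a Monday, no breaks.

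- 15 fractions: last fraction 18 days after the first; 18 + 14 = 32; 90 − 32 = 58 days (64% of 90).
- 40 fractions: last fraction 53 days after the first; 53 + 14 = 67; 90 − 67 = 23 days (26% of 90).

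These are shares of calendar time, not of risk.

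**The case against.** A reader might infer that the 90-day contact cannot produce a primary event, that late reactions are excluded by construction, and that the primary rate will be biased downward. The documents do not support that.

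- A *worsened* answer reaches the treating radiation oncologist, who is the assessor named in the primary outcome. That question covers the whole interval since the 2-week visit.
- Section 10.1 sends any adverse event during the study, including one volunteered by the subject, to the AE Source Doc. Section 13.2 counts events or reactions reported at the site and names no form or time limit. Under reading B, both can admit a late event.
- No late-event rate is given. Section 10.2 requires, for a probable rating, plausible timing, a compatible response to de-challenge, and other causes excluded or unlikely. With the dressing off for weeks and irradiation an obvious competing cause, few day-90 pain or itch answers may qualify.
- A primary count ending two weeks after RT, with a supplementary check at day 90, would also be compatible with the objective. Nothing in the documents says that FDA asked for 90-day data in the primary endpoint.

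All four points stand, and they limit the claim. They do not supply the missing steps. No text returns the oncologist's judgement from a *worsened* answer to the primary-outcome form, pain and itch go nowhere, and the helpful reading of section 10.1 depends on an end of study that the documents leave in conflict. That few late symptoms may be attributable is a reason to have the oncologist decide, not a reason to leave them unassessed.

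**Conclusion.** The point holds as a gap in the plan: no route is defined from the 90-day contact to the primary outcome. Followed as written, the schedule, questions and escalation rule would leave late pain or itch unattributed, and could miss a reaction that came and went. How a *worsened* case is handled is left to discretion.

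The size of any undercount is unknown. The movement from 0/36 to 1/36 shows sensitivity to one event and is not a forecast. The 23 to 58 days without a scheduled attribution form rest on the assumed five-fraction week; breaks in treatment would shorten the interval.

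One related limit: section 5.1 arranges the 90-day contact at the 2-week visit. Subjects who withdraw earlier stay in the intent-to-treat analysis but have no stated 90-day contact.

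**What to change.** - Mark the Weekly AE/Chart Review Source Doc in the 90-day column of the schedule.
- Add the existing question on adverse reactions to the dressing to the 90-day form and Appendix A, worded to cover the time since the 2-week visit.
- Have the radiation oncologist attribute any reported adverse reaction, worsening, pain or itch.
- State that adverse event monitoring runs to the 90-day contact, and reconcile sections 2.1, 5.2, 10.2 and 10.3 with the follow-up text in 5.1 and note 6 of section 15.
- Leave unchanged the fully evaluable definition (section 3.1) and the end of dressing use, both at two weeks post-RT. Simply redefining study completion as day 90 would disturb both: section 13.2 describes the 30 as subjects who fully complete the study, so a missed call could remove someone, and section 5.2 ties dispensing to completion.
- Report probable or definite events through two weeks post-RT and through day 90 for all treated subjects. State how many were reached at day 90, and how those who withdrew early are contacted.

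The cost is one question, one more use of an existing form, some oncologist time for attribution, and protocol wording. The reported event rate may look slightly less favourable.

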5.2. SILVERLON® DRESSING

Page 20 of 41 RSRB STUDY00004587 Version Date: 09/14/2021 NCT04238728

The device being evaluated is Silverlon® Burn/Wound Contact Dressings. The device has been commercially marketed since 2003 and has 16 FDA 510(k) clearances. Silverlon® has been used on hundreds of thousands of patients over the last 17 years. For this reason, the intervention is considered a non-significant risk device. This study is being conducted to provide safety data to the FDA to support an application to specify a radiation dermatitis indication for Silverlon® Dressings. For this study, Silverlon® Dressing will be supplied by Argentum Medical. Where possible, all product will come from a single lot. Product will be sent directly to the study coordinator or principal investigator at University of Rochester Medical Center. On conclusion of the study, any unused product will be returned to Argentum Medical. Study personnel will be responsible for storage and distribution of the Silverlon®. Storage will follow manufacturer's instructions which are: "Store Silverlon® Burn/Wound Contact Dressings in normal warehouse conditions. Keep dry. Avoid excessive heat or humidity (20). Each patient will receive the appropriate size of Silverlon® to cover the whole irradiated breast area. Subjects will receive two Silverlon® dressings at the start of the study. Since, Silverlon® dressings are indicated for use up to 7 days, two Silverlon® dressings will be dispensed to the subject every 7 days until completion of the study (i.e., 2 weeks (14 days) post-radiation therapy). The total number Silverlon® dressings dispensed to subjects will vary and be based on the length of their prescribed course of radiation therapy. Furthermore, additional Silverlon® dressing will be dispensed to the subject by request (i.e., due to loss, damage, ran through washing machine, etc.) as necessary for them to complete the study.

For this study, each subject will be instructed to wear the Silverlon® dressings for 7 days in the following manner:

- Silverlon® dressing should cover the whole irradiated breast area and kept in place by a bra.
- Start wearing Silverlon® dressing on the first day of radiation therapy
- Continue wearing until 2 weeks after completion of radiation therapy.
- Wear Silverlon® dressing all of the time except when bathing/showering, swimming, and during radiation treatment sessions. The dressing should be stored in a clean, dry resealable bag or container (e.g., ziplock bag) when not worn to protect it from becoming soiled of damaged.
- The radiation site can be washed daily with mild unscented soap (per instructions by the radiation oncologist).
- Use of any topical ointments, lotions, creams or gels with Silverlon® dressing during the course of the study is permitted under the guidance of the treating physician for subjects with worsening skin reactions to help prevent moist desquamation and subject withdrawal.
 - Silverlon® dressing is to be removed during the application of topical agents to the treatment area, and re-applied after total absorption of the topical agent into the skin (approximately one hour after application). Documentation of removal and reapplication of the Silverlon® dressing in the Subject Compliance Log for topical medication administration is required.
- Do not use Silverlon® dressing past expiration date on the product packaging.

5.3. OUTCOME MEASURES AND STUDY FORMS

Page 21 of 41 RSRB STUDY00004587 Version Date: 09/14/2021 NCT04238728 Eligibility Checklist: This paper form contains the inclusion and exclusion criteria for participation in this study. This form is completed to ensure eligibility for the trial. Study personnel obtaining consent will complete this form.

Screening Log: This electronic REDCap form will be used to document the eligibility of subjects, if the subject consented or declined participation, and reason for declining participation. The Screening Log will help create a CONSORT diagram at the completion of the study. This form will electronically capture screening information for the study and submit the information directly to the secure REDCap database at the University of Rochester Medical Center. Study personnel will access the form electronically through REDCap.

Study Reimbursement Form: This paper form is required along with a signed W9 for reimbursement of the adult caregiver in this study. The address on this form must match the signed W9 completed by the subject at the start of the study. After the consent process is completed, the subject (i.e., will print their name, mailing address, sign, and date this form, as well as complete a W9 form. At the end of the subjects' participation, the study coordinator or PI will circle the appropriate number of visits completed, indicate the number of visits completed, and indicate the amount to be reimbursed. A total of \$200 will be reimbursed for completion of all study procedures.

OnStudy Data Form: This is an electronic REDCap form that captures demographic information and medical history information on each subject. This form will be completed on paper or electronically and submit information directly to the secure REDCap database at the University of Rochester Medical Center. If completed on paper, the data will be entered into REDCap by study personnel. This form will collect the following:

- Subject ID
- On Study Date (Consent Date)
- Subject Initials
- Subject's First Name
- Subject's Last Name
- Subject's MRN
- Contact phone number
- Contact email (if preferred)
- Location of Radiation Therapy (Greece, WCI/SMH, Pluta)
- Age
- Race
- Ethnicity
- Marital Status
- Smoking status

- Alcohol use
- Prescription opioid use
- Breast size (i.e., bra size)
- Breast reconstructive surgery (yes/no)
- Tumor Stage (DCIS, I, II, III, IV)
- Chemotherapy Prior to Radiation (yes/no)
- Current hormone treatment (yes/no)
- Current Herceptin treatment (yes/no)
- Body Mass Index (BMI)
- Fitzpatrick Skin Type
- Surgery before RT (yes/no)
- Current Medications

Page 22 of 41 RSRB STUDY00004587 Version Date: 09/14/2021 NCT04238728 Weekly AE/Chart Review Source Doc: This is an electronic REDCap form for collection of any radiation treatment changes, skin changes, or adverse reactions documented by the treating radiation oncologist in the EMR chart note for the patient's weekly clinic visit. Study personnel will review the EMR chart note and report any documented any adverse reactions, skin changes, and/or radiation treatment changes in the form. The following information will be collected on the form:

- Changes in prescribed radiation treatment (yes/no; if "yes", then description of change)
- Documentation of skin changes in radiation treatment area (yes/no)
- Occurrence of adverse event in radiation treatment area to which Silverlon® dressing was applied
- Description of the adverse event
- Date of onset
- Serious (Yes/No)
- Intensity (Mild/Moderate/Severe)
- Relation to Study Drug (Definite/Probable/Possible/Unlikely/Unrelated)
- Action with Study Drug (No Action/Interrupted/Stopped Entirely).

Questions Log: This log will be an electronic REDCap form that collects the answers to the questions asked to the patient by phone, email, or in study visits (as preferred by the subject). Study personnel will ask the subject: 1) Are you wearing Silverlon dressing while you are sleeping? (yes/no); 2) Are you having any discomfort while wearing the Silverlon dressing? (yes/no); and 3) Are you having any adverse reactions to the Silverlon dressing? (yes/no). If the subject answers "yes" to question 3 regarding an adverse reaction to Silverlon, study personnel will document a description of this reaction in the space provided on the form.

RTOG Score: The RTOG toxicity criteria is one of the most commonly used scales for radiation-induced skin reactions (21, 22). The radiation oncologist will rate the skin reaction in the area where Silverlon® dressing was applied in person using the RTOG scale below. The RTOG scores will completed on paper and then entered electronically into REDCap:

RTOG SCALE

0	1	2	3	4	5
No change	Faint erythema,	Tender or bright	Confluent moist	Ulceration,	Death
	dry	erythema,	desquamation in	hemorrhage,	
	desquamation,	moderate	areas other than	necrosis	
	epilation,	edema, patchy	in skin folds,		
	decreased	moist	pitting edema		
	sweating	desquamation			

Page 23 of 41 RSRB STUDY00004587 Version Date: 09/14/2021 NCT04238728 Radiation Induced Skin Reaction Assessment Scale (RISRAS): This scoring system contains both a healthcare professions assessment scale and a patient symptom scale (23). The healthcare professional assessment scale individually scores the extent and severity of erythema, dry desquamation, moist desquamation, and necrosis using a 5-point scale from 0 to 4. Erythema is rated based on the degree of color change. Dry desquamation, moist desquamation, and necrosis are rated based on the percentage of the treatment area affected by that particular reaction. The patient component focuses on skin tenderness, itching, burning, and functional activity using a 4-point scale from 1 to 4. The Healthcare Professional Assessment Scale scores and the Patient Symptom Scale scores are added together for a total skin reaction score. The higher the score, the worse the skin reaction. The Healthcare Professional Assessment Scale will be completed by the radiation oncologist in person at Mid-Study Visit, EndRT Visit, and 2-Week Post-RT Visit. The Patient Symptom Scale will be completed by the subject at the Mid-Study Visit, EndRT Visit, and 2-Week Post-RT Visit. Study personnel will enter the data from the completed forms into REDCap.

HEALTHCARE PROFESSIONAL ASSESSMENT SCALE

HEREITICHE THOI ESSIONAL HESSESSANETT SCHEE						
	0	1	2	3	4	
Erythema (E)	Normal Skin	Dusky pink	Dull red	Brilliant red	Deep red/purple	
Dry Desquamation (DD)	Normal Skin	<25%	>25-50%	>50-75%	>75-100%	
Moist Desquamation (MD)	Normal Skin	<25%	>25-50%	>50-75%	>75-100%	
Necrosis (N)	Normal Skin	<25%	>25-50%	>50-75%	>75-100%	

PATIENT SYMPTOM SCALE

	Not at all	A little	Quite a bit	Very much
Tenderness,				
Discomfort, or	1	2	3	4
Pain?				
Itch?	1	2	3	4
Burning sensation?	1	2	3	4
Skin reaction				
interfered with day	1	2	3	4
to day activities?				

Page 24 of 41 RSRB STUDY00004587 Version Date: 09/14/2021 NCT04238728 Dermatology Life Quality Index (DLQI): This is a self-report 10-item questionnaire that measures how much a skin problem (i.e., radiation dermatitis) has affected the subject's quality of life (24, 25, 26). Subjects will be asked 10 questions about how their skin problem has affected different aspects of their life over the last week. Subjects will respond on a 4-point scale: 0 = Not at all; 1 = A little; 2 = A lot; and 3 = Very much. Subjects can also state whether a question is "not relevant," which will be scored as 0. The DLQI is scored by summing the score of each question resulting in a maximum of 30 and a minimum of 0. The higher the score, the more quality of life is impaired. Scores will be interpreted for overall effect on subject's quality of life: 0-1 = no effect; 2-5 = small effect; 6-10 = moderate effect; 11-20 = very large effect; 21-30 = extremely large effect. This questionnaire will be completed by subjects on paper during each study visit:

- Baseline Visit
- Mid-Study Visit
- EndRT Visit
- 2-Week Post-RT Visit

Digital Photographs of Skin:

Figure 2: Four location within the breast radiation area

Medial/Front

Lateral (side-view)

Axilla Inframammary fold

Digital photographs (i.e., images) will be taken of the irradiated skin of the whole breast to which Silverlon® dressing was applied. Images of three different locations (medial/front breast, lateral breast, and inframammary fold,) will be captured within the RT site during the Baseline Visit, Mid-Study Visit, EndRT Visit, and 2-Week Post-RT Visit (Figure 2). The Baseline Visit photographs will be to image the skin prior to application of Silverlon® dressing. Digital photographs will be taken of areas where Silverlon® dressings were applied within the radiation treatment area. The photographs should document the severity of radiation dermatitis and be representative of the RTOG score given to a subject for that specific time point. Do not exceed 4 photographs for each time point for each subject (i.e., Baseline Visit, Mid-Study Visit, EndRT Visit, and at 2-Week Post-RT

Visit per subject). These digital photographs will only be used for this study and will not be included in subject's medical record. The digital photographs will be de-identified (i.e., only labeled with Study ID and assessment week). During the study, the digital photographs will be stored on a password-protected, desktop computer in a locked office by [name]. Upon completion of the study, the digital photographs will be stored at the University of Rochester.

Digital images will be taken with an Apple 7th Generation iPad camera. The iPads will be used for data collection and locked down for utilization of REDCap and University's Box app. The digital images will be stored directly into Box, which is password-protected, secure on the University network, and HIPAA compliant. Study personnel will take a "close-up" image of the skin that is in focus. Study personnel will avoid shadowing of the skin in the images. The photographs will be taken at these time points:

- Baseline Visit
- Mid-Study Visit
- EndRT Visit
- 2-Week Post-RT Visit

Page 25 of 41 RSRB STUDY00004587 Version Date: 09/14/2021 NCT04238728 Withdrawal Form: This electronic REDCap form will be used to document the time and reasons for withdrawals during the study. The data from this form will be electronically entered into the secure REDCap database at the University of Rochester Medical Center.

Comprehensive Study Log: This is a password-protected excel spreadsheet that contains a log for all subjects in the study. The information kept in this file include: Subject ID, Subject Name, Subject MRN, Screened & Eligible, Consent Completed, Screen Fail, Size Silverlon® dispensed, Baseline Complete, Weekly Phone Calls Completed, Mid-Study Visit Complete, EndRT Visit, 2-Week Post-RT Visit Completed, Completed Study, Withdrawn, and Loss to Follow-up. Study personnel will complete the required subject information (i.e., dates, etc.) and check the appropriate boxes (i.e., completed = green fill; incomplete = red fill) as the study progresses to monitor subject participation in the study.

EndRT Data Form: This is an electronic REDCap form for the collection of final radiation therapy information for each subject. The information on the form includes: RT Type (conventional vs. short-course), positioning (prone vs. supine), total radiation dose, fractionation, breast field separation (cm), boost dose (if any), bolus (if used), and any delays in RT. Study personnel will enter the data electronically into the secure REDCap database at the University of Rochester Medical Center.

Silverlon® Compliance Log: This is a paper form on which the subject will document each time they remove the Silverlon® dressing and apply the Silverlon® dressing. The subject will also indicate the reason for removal of Silverlon® dressing (i.e., radiation treatment session, bathing/showering, swimming, or other. If the subject selects "other" for removal, the subject should describe the reason in the space provided). This is a paper form that the subject will take home with them and complete as necessary daily whenever the Silverlon® dressing is removed and put back on. The subject will be given a new Compliance Log every 7 days with the two new Silverlon® Dressings. The subject will return their completed log to study personnel every 7 days.

Silverlon® Accountability Record: This is a paper form that will be kept with the provided Silverlon® dressings in Radiation Oncology at University of Rochester. This form will record: the size and number of the dressings in stock, the dispense date of any dressings, Subject ID for dispensed dressings, initials of study personnel, number of dressings dispensed, and adjusted number of dressings in stock. This form will be completed each time Silverlon® dressings are dispensed to a study subject.

90-Day Phone Call Form: This is an electronic REDCap form collects the answers to the questions asked during the 90-Day Follow-Up that will occur 90 days after the start of RT. Study personnel will ask the subject: 1) Since your 2-Week Post-RT visit, has your skin reaction in the area where the Silverlon® dressing was applied improved, stayed the same, or worsened?; 2) Do you have any skin pain in the area where the Silverlon® dressing was applied? (yes/no); 3) Do you have any itching in the area where the Silverlon® dressing was applied? (yes/no); 4) Do you feel like your skin in the radiation treatment area has fully recovered? (yes/no); and 5) Would you recommend Silverlon® dressing to other patients during radiation therapy? (yes/no). For question 1, if the subject answers "worsened", study personnel will document the description of

Page 26 of 41 RSRB STUDY00004587 Version Date: 09/14/2021 NCT04238728 the skin reaction in the provided area on the form and will notify the treating radiation oncologist.

